5.3.5 Other safety parameters

5.3.5.1 Height and Body Mass Index (BMI)

Height and weight will be measured at the time points indicated in the Flow Chart.

Height should be measured using the same stadiometer for one patient.

SDS (Standard Deviation Score), e.g. z-score, values for height and BMI will be calculated by the sponsor for the statistical analysis using the WHO age-specific references.

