## **5.4 OTHER VARIABLES**

#### **5.4.4 Safety data**

The SBP and DBP will be derived for use in the statistical analysis as the mean of all available SBP and DBP readings, respectively, at the same visit.

Standard adverse event attributes (seriousness, intensity, relationship of AEs, AEs leading to study medication discontinuation), laboratory endpoints, vital signs and BMI z-score will be analysed.

For the full definition of safety endpoints, refer to CTP Section 5.3.

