#### 6.7 BASELINE, TIME WINDOW, AND CALCULATED VISITS

The term “baseline” refers to the following definitions according to the individual analysis period.

- *Study baseline*: Last observed measurement prior to administration of any initially randomised study medication at Day 1.
- *Titration baseline*: Last observed measurement prior to administration of the re-randomised study medication for the initial empagliflozin patients at Week 14. If last observed measurement is after rescue medication then there is no titration baseline for OC analysis.
- *Safety extension baseline*: Last observed measurement prior to administration of the re-randomised study medication for the initial placebo patients at Week 26.

Note: On or prior to date of randomisation will be used, instead of prior to date of drug administration, for randomised patients who have not taken any blinded study drug.

Both date and time of administration of the randomised study medication are expected to be recorded at Day 1, Week 14 and Week 26. In the determination of baseline for a parameter, if the parameter of interest:

- is collected with date and time: both date and time are used in the calculation of ‘last observed measurement prior to administration’. If the dates and times are equal, the parameter will be determined to be prior to administration.

- is collected with only date: the dates are equal, the parameter will be determined to be prior to administration.

The exception to this rule, is HbA1c, whereby even though time of sample is collected, it will be handled as if it was collected only with date.

Measurements taken after the first intake of randomised study drug will be considered on-treatment values if they have been obtained up to the end of the endpoint specific follow-up period as defined in [Table 6.7: 1](#).

Table 6.7: 1 Endpoint specific follow-up period for the assignment to treatment phase

Endpoint	Last day of assignment to treatment phase (days after study drug stop date)
Efficacy	
HbA1c	7
FPG	1
Body weight	1
BMI z-score	1
Blood pressure (systolic, diastolic)	1
UACR	7
Safety	
Adverse events	7
AESI Hepatic injury 	30
AESI Lower limb amputation	End of study
Safety laboratory measurements	7
AST/ALT/TBILI 	30
Pulse rate	1
C-peptide	1
Tanner staging	1

[1] Refers to a specific safety analysis including all hepatic injuries with an onset date up to 30 days after the study treatment stop.

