#### 7.8.2.1 General laboratory evaluation

The following general laboratory evaluations will be performed for all laboratory data captured in the study including bone metabolism biomarkers (Calcium, phosphate, alkaline phosphatase, 25-OH-vitamin D, intact parathyroid hormone, serum N-terminal cross-linked telopeptide (NTx)). But excluding HBA1C, FPG, C-peptide and UACR that are separately

described in the planned efficacy analysis, and other biomarkers that are separately described in [Section 7.8.2.3](#), [7.8.2.4](#) and [7.8.2.5](#)):

- For quantitative lab results, descriptive statistics per treatment group at baseline, last value on-treatment, and change from baseline to last value on-treatment (in both SI and conventional units)
  - If both the BI adult standard and the central lab standard ranges are available, the descriptive statistics will be performed on the normalised value.
    - Exception to NTx: the central lab standard range of female with tanner stage 5 will be used as the BI standard reference range.
  - Otherwise, the descriptive statistics will be performed on the standardised value
- For qualitative lab results, frequency tables per treatment group will be presented at baseline and at last value on treatment (only in SI unit).
  - Erythrocytes and leukocytes in urine analysis will be analysed as categorical data with 2 categories (“Normal” and “High”).
- Frequency table per treatment group will summarise the number of patients within and outside the reference range at baseline and the last measurement on treatment (only in SI unit).
  - The age dependent reference range used for post-baseline values by the lab will be replaced by the reference range as provided for the respective patients' baseline measurement, and re-categorised.
  - Exclude parameters only measured occasionally.
- Frequency tables (include a patient listing) per treatment group will summarise the number of patients with any potentially clinically significant abnormality (PCSA) using company standard clinically significant criteria. PCSA will be determined based on SI units and only be counted in tables if the patient had no PCSA value at baseline.

All the above analyses will be performed on the appropriate treated set for TG1 and TG5. The PCSA tables will additionally be produced for TG6 and TG4 (from Week 14 up to Week 52).

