			5.2.2, 5.3.1	Updated “Proportion of patients who achieve HbA1c goals ...” to “Proportion of patients who achieve HbA1c ...”. To follow CTP.
			5.3.1	For proportion of patients who initiate glycaemic rescue therapy up to 26 weeks and 52 weeks, the word “(insulin)” has removed from DINAMO criteria and “(metformin and/or insulin)” has removed from DINAMO MONO criteria as to include all antidiabetic therapies as rescue medications and not limited to the allowed ones.
			5.3.2	Updated “Adverse events (AE) up to 26 and 52 weeks, including adverse events of special interest (AESI) (see CTP Section 5.3.6.1)” to “Adverse events (AE) up to 26 and 52 weeks, including adverse events of special interest (AESI) (see CTP Section 5.3.6.1), genital infections, urinary tract infections, acute pyelonephritis or urosepsis, bone fracture, arthralgia, bullous pemphigoid, adverse events related to reduced intravascular volume and ketone measurements reported as AE”.
			5.4.1	Updated the following texts to align with project level reporting. Old text” For analysis purposes, BMI will also be derived at visits where only weight was collected, using the last available height that was reported prior to the date of weight measurement.” to New text “For analysis purposes, BMI will also be derived at visits where only weight was collected, using the last available height that was reported prior to the date of weight measurement. In case of missing height at screening, height can be carried backward for the derivation. ”  Old text “The age in month at Screening will be used to determine the values of L, M and S.” to New text “The age in month at informed consent will be used to determine the values of L, M and S.”.

Table 10: 4 History table for TSAP revised version dated 7th Jul 2022 (continue)

Version	Date	Author	Changes in old Section (new Section)	Brief description of change

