			All sections	
Updated “AGE” to “age at randomisation” for all AGE in category, as this is the correct time point. And “AGE” to “age at inform consent” for all continuous AGE.

			7.8.2.3	
Added the conventional unit tables according to FDA request: “All analyses in this section will be repeated for parameters in conventional unit and presented in Appendix 16.1.13.”.

Table 10: 4 History table for TSAP revised version dated 7th Jul 2022 (continue)

Version	Date	Author	Changes in old Section (new Section)	Brief description of change
Revised	7-JUL-2022		7.8.2.4	Updated the following text with the bold text to clarify what UACR values are used. "A shift table from baseline value to last and maximum values on-treatment will be provided based on the following UACR categories (which used the derived UACR and not the albumin/creatinine ratio values provided by the lab): normal ..."  Also added the derived UACR formula.
			7.8.2.5	Added PINP to the biomarkers descriptive tables.  Added additional tables "Descriptive statistics by sex and tanner stage category version 2, see Table 6.4:1 for the category, will be summarised over time up to Week 26 by TG1 and up to Week 52 by TG5 on the standard units for PINP, NTx, IGF-1, IGF-BP3."
			8	Old text "001-MCS-36-472: "Standards and processes for analyses performed within Clinical Pharmacokinetics/Pharmacodynamics", current version; IDEA for CON" to New text "BI-KMED-TMCP-MAN-0012: "Standards and processes for analyses performed within Clinical Pharmacokinetics/Pharmacodynamics", current version; KMED".

Table 10: 5 History table for TSAP revised version dated 28th Jul 2022

Version	Date	Author	Changes in old Section (new Section)	Brief description of change
Revised	28-JUL-2022		7.4.1.1	Updated to use one seed for the missing data imputation for all confirmatory analyses. OLD Text ... The seed used in the DINAMO primary family of analyses will be 1218009101. NEW Text ... The seed used in the DINAMO confirmatory analyses will be 1218009101.
			7.4.1.2	Removed the seeds from this section in order to use the seed mentioned in section 7.4.1.1. Deleted OLD Text ... The seeds used in the DINAMO secondary family of analyses will be 1218009102 for hypothesis H'0,1 and 1218009103 for hypothesis H'0,2.

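### The SAP takes L, M and S for the BMI z-score at age of informed consent with no exception for later visits, so post-baseline z-scores use a reference that is too young

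*SAP*

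**What the plan says.** Protocol 5.3.5.1 promises standard deviation scores for height and BMI "using the WHO age-specific references". It does not say at which age the reference is read.

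The public text does not show the body of SAP 5.4.1, but the history table in SAP Section 10 gives the wording adopted on 7 July 2022. The age in months at informed consent, which replaced age at screening, "will be used to determine the values of L, M and S". The same entry says that "BMI will also be derived at visits where only weight was collected, using the last available height", so BMI exists at visits after baseline. The only later revision, on 28 July 2022, lists changes to 7.4.1.1 and 7.4.1.2 alone ("Updated to use one seed for the missing data imputation for all confirmatory analyses"). The consent-age sentence is therefore in force.

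Two visible places show that the z-score is used after baseline:

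- SAP 5.4.4 says that "laboratory endpoints, vital signs and BMI z-score will be analysed".
- SAP Table 6.7: 1 ("Endpoint specific follow-up period for the assignment to treatment phase") lists BMI z-score with a limit of one day after the study drug stop date. Only post-baseline values need such a limit.

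**The concern.** A z-score is used in growing children because it removes normal growth: each value is set against peers of the same age on the day of measurement. If L, M and S stay at their consent values, every later z-score for that child is a fixed transform of raw BMI. It then adds nothing to the raw BMI already summarised under SAP 7.8.3, while its label suggests that age has been taken into account.

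Patients are 10 to 17 years old at randomisation, and follow-up on treatment lasts 52 weeks. Where the reference rises over that time, normal growth appears as a rising z-score and can mask part of a true fall. Where there is a concurrent placebo group, the drift is common to the arms and largely cancels. The long-term safety analysis in SAP 7.8 (treatment grouping 5, to Week 52) excludes patients first randomised to placebo, so a within-arm change there has nothing to cancel against.

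**Working it through.** There is no figure in the plan to reproduce. The check has two parts.

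**1. How far the reference age lags the measurement (flow chart).** Consent is given at Visit 1A, planned 21 to 14 days before randomisation and allowed up to 28 days before. Week 26 is 182 days after randomisation and Week 52 is 364 days after.

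| Visit | Shortest lag | Longest lag | With the +7 day visit window |
|---|---|---|---|
| Week 26 | 182 + 14 = 196 days | 182 + 28 = 210 days | 217 days (31 weeks) |
| Week 52 | 364 + 14 = 378 days | 364 + 28 = 392 days | 399 days (57 weeks, about 13 months) |

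**2. What the lag does to a child who stays on one centile.** Let the child's true z be constant, hold L and S constant, and let the reference median rise from M₀ at consent to Mₜ at the visit. The z-score computed with consent values is

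z_fixed = [ (Mₜ/M₀)^L × (1 + L·S·z) − 1 ] / (L·S).

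With values taken at the age of measurement the change is zero by construction. The spurious change is z_fixed − z.

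*Assumed inputs, not in the documents:* median BMI rising 1% to 5% a year, L from −2.5 to −1.5, S from 0.11 to 0.15.

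Example: 85th percentile (z = 1.036), L = −2, S = 0.13, median rising 3% a year, lag 392 days.

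- Mₜ/M₀ = 1.03^(392/365.25) = 1.0322, and 1.0322^(−2) = 0.9385.
- 1 + L·S·z = 1 − 0.26 × 1.036 = 0.7306.
- z_fixed = (0.9385 × 0.7306 − 1)/(−0.26) = 1.209, a spurious rise of 0.17 SD.

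Over the full grid, with lags of 210 and 392 days:

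| True z | Week 26 | Week 52 |
|---|---|---|
| 1.036 | +0.02 to +0.21 | +0.04 to +0.38 |
| 2 | +0.01 to +0.17 | +0.02 to +0.31 |
| 3 | +0.00 to +0.13 | +0.00 to +0.23 |

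At z = 3 the combination L = −2.5, S = 0.15 is left out because 1 + L·S·z is negative.

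A cruder check agrees. If reference BMI at the child's centile rises 0.5 to 1.2 kg/m² a year and one z unit spans 4 to 7 kg/m² (again assumed), the drift is 0.5/7 = 0.07 to 1.2/4 = 0.30 SD a year.

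**For scale.** Protocol 1.2.1 cites an adult weight reduction on empagliflozin of up to 2.2 kg against placebo. At an assumed height of 1.60 m that is 2.2/1.60² = 0.86 kg/m². With the same 4 to 7 kg/m² per z unit it is 0.86/7 = 0.12 to 0.86/4 = 0.21 SD. The artefact can be as large as a plausible effect, and it runs the other way.

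**The case against.** **The rule is read from a history table.** The body of SAP 5.4.1 and the further-endpoint sections are not public, and adjoining text might treat later visits differently. This limits certainty. But the sentence is recorded as new text, carries no visit qualifier, and sits in the entry that derives BMI at later visits. No reading of it as it stands makes a later z-score correct.

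**No z-score change table is visible.** This stands. The one explicit z-score output in the public text is the baseline table (SAP 7.1.1). SAP 7.8.3 summarises raw BMI over time, and the endpoint in Protocol 5.1.3.2 is BMI in kg/m². A reader might infer that an uncontrolled 52-week table of z-score change is certain to be produced. The documents show only that on-treatment z-scores are analysed, not in which table.

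**The size rests on assumptions.** This also stands. The low end is negligible. Between 30% and 70% of patients are to be under 15, so the age mix matters and has not been modelled.

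**The laboratory ranges.** A reader might infer that SAP 7.8.2.1 makes the same mistake, because "The age dependent reference range used for post-baseline values by the lab will be replaced by the reference range as provided" for the patient's baseline measurement. That is a trade-off, not an error. One fixed range keeps the baseline and last-value categories comparable, whereas a range by age at sampling lets a constant value change category when a child crosses an age cut. The rule is stated only for the table of values within and outside the range. It is not stated for the tables of potentially clinically significant abnormalities. PINP, NTx, IGF-1 and IGF-BP3 are also summarised by sex and Tanner stage (SAP 7.8.2.5).

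**Conclusion.** The point holds for the BMI z-score, at low severity. As written, the rule sets post-baseline values against a reference 196 to 210 days too young at Week 26 and 378 to 392 days too young at Week 52, before visit windows. These lags follow from the flow chart. That drift follows from the lag is algebra, given a reference that rises with age. Its size, about 0.02 to 0.4 SD at Week 52 for z between 1.036 and 2 and less at z = 3, depends on assumed reference values.

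The consequence is confined to within-arm change in z-score, especially in any summary to Week 52 without placebo. A reader might infer that the efficacy conclusions are biased. They are not: HbA1c does not use the z-score, body weight is compared with placebo in its own right, and drift in the z-score at Week 26 is shared by the randomised arms.

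**What to change.** In SAP 5.4.1, take L, M and S at the child's age in months on the date of each BMI measurement, and keep age at informed consent for the screening or baseline value only. If the consent-age sentence was always meant for baseline alone, say so and state the age used afterwards.

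The cost is one sentence and minor reprogramming. The rule needs only age on the measurement date, from birth data and visit dates already held. The real downside is a departure from the project-level reporting convention that the history table gives as the reason for the July 2022 change. If outputs must match that convention, the consent-age version can be kept as a supporting display.

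SAP 7.8.2.1 needs no change. A version of the range table by age at sampling could be added as a supporting table if wanted.
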